6.6 Overdose

An overdose is defined as the accidental or intentional administration of any dose of a product that is considered of both excessive and specifically important.

All occurrences of overdose must be reported as SAEs (see [Section 6.1.1](#) for reporting details).

6.7 Potential Drug Induced Liver Injury (DILI)

Wherever possible, timely confirmation of initial liver-related laboratory abnormalities should occur prior to the reporting of a potential DILI event. All occurrences of potential DILIs, meeting the defined criteria, must be reported as SAEs (see [Section 6.1.1](#) for reporting details).

Potential drug induced liver injury is defined as:

1. AT (ALT or AST) elevation > 3 times upper limit of normal (ULN)

AND

2. Total bilirubin > 2 times ULN, without initial findings of cholestasis (elevated serum alkaline phosphatase),

AND

3. No other immediately apparent possible causes of AT elevation and hyperbilirubinemia, including, but not limited to, viral hepatitis, pre-existing chronic or acute liver disease, or the administration of other drug(s) known to be hepatotoxic.

6.8 Other Safety Considerations

Any significant worsening noted during interim or final physical examinations, electrocardiogram, x-ray filming, any other potential safety assessment required or not required by protocol should also be recorded as a nonserious or serious AE, as appropriate, and reported accordingly.

7 DATA MONITORING COMMITTEE AND OTHER EXTERNAL COMMITTEES

Not applicable to this study.

8 STATISTICAL CONSIDERATIONS

8.1 Sample Size Determination

Approximately 346 subjects will be randomized to the 2 treatment arms in a 1:1 ratio in order to target 340 treated subjects (170 per arm). Given a two-sided alpha of 0.05, this number of treated subjects provides 80% power to show a statistically significant difference in the rate of drug-related Grade 3 - 5 AEs between the two treatment arms, assuming a rate of 40% in Arm A and a rate of 55% in Arm B.

We assume that treatment with N3I1 (Arm A) will result in a 15% reduction in the rate of drug-related Grade 3 - 5 events when compared to treatment with N1I3 (Arm B). The difference of 15% is clinically meaningful and assumes a 40% event rate in Arm A and a 55% event rate in Arm B. The assumption of 55% in Arm B is based on observed rates of drug-related Grade 3 - 5 AEs in the combination arm of studies CA209069 and CA209067, which enrolled the same patient population as the current study (previously untreated metastatic melanoma). The assumed reduction to 40% in Arm A corresponds to the same rate ratio (0.727) that was observed in Cohort 2a relative to Cohort 2 in Study CA209004.

Table 8.1-1 shows the precision that the sample size of 170 treated subjects per arm will provide for estimating adverse event rates (primary endpoint) or objective response rates (secondary endpoint), under different assumed observed rates.

For example, if exactly 68 of 170 treated subjects (40%) experience a drug-related Grade 3 - 5 AE in Arm A and 94 of 170 treated subjects (55.3%) experience a drug-related Grade 3 - 5 AE in Arm B, then the exact 95% CI for the rate of drug-related Grade 3 - 5 AEs will be (32.6%, 47.8%) for Arm A and (47.5%, 62.9%) for Arm B.

Furthermore, if exactly 102 of 170 treated subjects (60%) experience an objective response in a treatment arm, then the exact 95% CI for the ORR in that treatment arm will be (52.2%, 67.4%). If the observed ORR is exactly the same in each arm and equal to 60%, then the 95% CI for the difference in ORR between arms will be (-10.4%, 10.4%), and the 95% CI for the odds ratio will be (0.65, 1.54).

Table 8.1-1: Exact 95% CI for Rates when Observed in 170 Subjects			
Number Subjects with Event	Observed Rate	Lower limit Exact 95% CI	Upper limit Exact 95% CI
68	40.0%	32.6%	47.8%
77	45.3%	37.7%	53.1%
85	50.0%	42.2%	57.8%
94	55.3%	47.5%	62.9%
102	60.0%	52.2%	67.4%

8.2 Populations for Analyses

Since the primary objective will be addressed by a safety endpoint, the primary endpoint analysis will be based on all treated subjects. For consistency, the secondary endpoints will use the same analysis population as the primary endpoint (ie, all treated subjects).

- All Enrolled Subjects: All subjects who signed an informed consent form and were registered into the IRT.
- All Randomized Subjects: All subjects who were randomized to any treatment group. This is the primary dataset for efficacy listings
- All Treated Subjects: All subjects who received at least one dose of any study medication. This is the primary dataset for analysis of study conduct, study population, efficacy (including secondary endpoints), exposure, and safety (including primary endpoint).
- PK Subjects: All treated subjects with available serum time-concentration data.
- Immunogenicity Subjects: All treated subjects with available ADA data.
- Biomarker Subjects: All treated subjects with available biomarker data.

8.3 Endpoints

8.3.1 Primary Endpoint(s)

The primary endpoint of the study is the rate of drug-related Grade 3 - 5 AEs. The drug-related Grade 3 - 5 AE rate is defined as number of subjects who experienced at least 1 AE of Grade 3 or higher, judged to be related to study drug by the investigator, and with onset on or after the first dose of study treatment and within 30 days of the last dose of study treatment, divided by number of treated subjects. AE grade will be defined using National Cancer Institute Common Terminology Criteria for Adverse Events (NCI CTCAE) version 4.0 criteria.

The analysis of the primary endpoint will occur when all subjects who are still on-treatment have had at least 2 post-baseline tumor assessments.

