3.1.2 Treatment Phase

- Begins with the randomization call to the IRT.
- Subject will be randomized to:
 - Arm A (N3I1): nivolumab 3 mg/kg + ipilimumab 1 mg/kg administered every 3 weeks for 4 doses or
 - Arm B (N1I3): nivolumab 1 mg/kg + ipilimumab 3 mg/kg ipilimumab are administered every 3 weeks for 4 doses.
- After combination therapy, all subjects will receive a flat dose 480 mg nivolumab IV every 4 weeks, beginning 6 weeks after the last combination dose, until progression or unacceptable toxicity.
- Treatment with Nivolumab will be limited to 2 years maximum duration.
- A negative pregnancy test should be documented within 24 hours prior to start of each dose of investigational product.
- Within 3 days from randomization, the subject must receive the dose of study medication.
- On study laboratory assessments should be drawn within 72 hours prior to dosing
- PK samples and immunogenicity samples will be collected according to the schedule in [Table 5.1-2](#) and [Table 5.1-3](#)
- Adverse event assessments should be documented at each clinic visit.
- Quality of Life will be assessed using European Organisation for Research and Treatment of Cancer Quality Of Life Questionnaire-core 30 (EORTC QLQ-C30) and European Quality of Life-5 Dimensions (EQ-5D) questionnaires, to be completed after randomization, prior to the first dose of study therapy and every 6 weeks for the first 6 months, and every 4 weeks until approximately week 40, according to the schedule in [Table 5.1-2](#).
- Study drug dose may be delayed for toxicity. See [Section 4.4.1](#).
- Treated subjects will be evaluated for response according to the RECIST 1.1 guidelines beginning 12 weeks (± 1 week) after randomization and continuing every 8 weeks (± 1 week) for the first 12 months, and then every 12 weeks (± 2 week) until disease progression or treatment discontinuation, whichever occurs later.
- This phase ends when the subject is discontinued from study therapy. For a complete list of reasons for treatment discontinuation, see [Section 3.5](#).

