4.4.4 Discontinuation Criteria

All discontinuation criteria apply for nivolumab and ipilimumab in both Arms A and B (during Part 1) given the blinded nature of this study.

Treatment should be permanently discontinued for the following:

- Any Grade 2 drug-related uveitis, eye pain or blurred vision that does not respond to topical therapy and does not improve to Grade 1 severity within the re-treatment period OR requires systemic treatment.
- Any Grade 3 non-skin, drug-related adverse event lasting > 7 days or recurs, with the following exceptions for laboratory abnormalities, drug-related uveitis, pneumonitis, bronchospasm, diarrhea, hypersensitivity reactions, infusion reactions and endocrinopathies:
 - Grade 3 drug-related uveitis, pneumonitis, bronchospasm, diarrhea, colitis, neurologic toxicity, hypersensitivity reaction, or infusion reaction of any duration requires discontinuation
 - Grade 3 drug-related endocrinopathies adequately controlled with only physiologic hormone replacement do not require discontinuation. Adrenal insufficiency requires discontinuation, regardless of control with hormone replacement.
 - Grade 3 drug-related laboratory abnormalities do not require treatment discontinuation except:
 - Grade 3 drug-related thrombocytopenia > 7 days or associated with bleeding requires discontinuation
 - Any drug-related liver function test (LFT) abnormality that meets the following criteria require discontinuation:
 - Grade ≥ 3 drug-related AST/ALT or Total Bilirubin abnormality
 - Concurrent AST or ALT > 3 x ULN and total bilirubin > 2 x ULN
- In most cases of Grade 3 AST or ALT elevation, study drugs) will be permanently discontinued. If the investigator determines a possible favorable risk/benefit ratio that warrants

continuation of study drug(s), a discussion between the investigator and the BMS Medical Monitor/designee must occur.

- Any Grade 4 drug-related adverse event or laboratory abnormality (including, but not limited to creatinine, AST, ALT, or total bilirubin), except for the following events which do not require discontinuation:
 - Grade 4 neutropenia \leq 7 days
 - Grade 4 lymphopenia or leucopenia
 - Isolated Grade 4 amylase or lipase abnormalities that are not associated with symptoms or clinical manifestations of pancreatitis.
 - Isolated Grade 4 electrolyte imbalances/abnormalities that are not associated with clinical sequelae and are corrected with supplementation/appropriate management within 72 hours of their onset

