4.5 Selection and Timing of Dose for Each Subject

The dosing regimen and schedule for Parts 1 and 2 are detailed in Table 4.5-1 and Table 4.5-2, respectively.

Note: The first flat dose 480 mg nivolumab in Part 2 will be administered 6 weeks after the last combination dose in Part 1.

Table 4.5-1: Dosing Schedule for Part 1 (Double-Blinded)				
Every 3 weeks dosing 1 cycle = 3 weeks				
	Cycle 1	Cycle 2	Cycle 3	Cycle 4
Arm A	Nivolumab 3 mg/kg Ipilimumab 1 mg/kg	Nivolumab 3 mg/kg Ipilimumab 1 mg/kg	Nivolumab 3 mg/kg Ipilimumab 1 mg/kg	Nivolumab 3 mg/kg Ipilimumab 1 mg/kg
Arm B	Nivolumab 1 mg/kg Ipilimumab 3 mg/kg	Nivolumab 1 mg/kg Ipilimumab 3 mg/kg	Nivolumab 1 mg/kg Ipilimumab 3 mg/kg	Nivolumab 1 mg/kg Ipilimumab 3 mg/kg

Table 4.5-2: Dosing Schedule for Part 2 (Open Label)	
Every 4 weeks dosing 1 cycle = 4 weeks, Cycle 5 to begin 6 weeks after Cycle 4 ^a	
	Cycle 5 and beyond
Arms A and B	Flat dose 480 mg nivolumab

^a Cycle X - Cycle 8, 9, etc until disease progression or unacceptable toxicity or a maximum treatment of 2 years.

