Review of Concomitant Medications	X	
Laboratory Tests	X	Within 72 hrs prior to dosing to include CBC w/ differential, LFTs, BUN or serum urea level, creatinine, Ca, Mg, Na, K, Cl, LDH, Glucose, amylase, lipase, TSH (+ reflex Free T4 and Free T3), albumin if clinically indicated).
Pregnancy Test (WOCBP only)	X	Serum or urine within 24 hours prior to administration of first dose and every 3 weeks thereafter in Part 1 of the study.
Pharmacokinetic and Immunogenicity Assessments		
Immunogenicity blood sample	See Section 5.5 for details regarding specific sample timing	
PK Samples	See Section 5.5 for details regarding specific sample timing	

Table 5.1-2: On-Study Assessments Part 1 (CA209511)		
Procedure	For Part 1, Study Drug Every 3 Weeks for 4 Cycles (Both Arm A and Arm B)	Notes
	Cycle 1, 2, 3, 4 (Day 1)	
Exploratory Biomarker Testing		
Exploratory Serum Biomarkers	X	To be collected pre-dose; before first 4 combination doses only.
Peripheral Blood Mononuclear Cells (PBMCs)	X	To be collected pre-dose; before first 4 combination doses only. To be collected in USA and Canada only.
Whole Blood Sample (DNA)	X	X = before first combination dose only.
Myeloid-Derived Suppressor Cell (MDSCs)	X	To be collected pre-dose; before the first and the third combination dose only
Efficacy Assessment		
Tumor Assessment	See Notes	FIRST tumor assessment should be performed at 12 weeks (\pm 1 wk) following randomization. CT Chest, CT (or MRI) abdomen, pelvis and all known sites of disease. Use same imaging method as was used at screening/baseline. Subjects with a history of brain metastasis should have surveillance MRI approximately every 12 weeks, or sooner if clinically indicated

Table 5.1-2: On-Study Assessments Part 1 (CA209511)		
Procedure	For Part 1, Study Drug Every 3 Weeks for 4 Cycles (Both Arm A and Arm B)	Notes
	Cycle 1, 2, 3, 4 (Day 1)	
Outcomes Research Assessments		
EORTC QLQ-C30 and EQ-5D	X	To be completed at the start of the clinic visit every 6 weeks. First questionnaire should be completed after IRT randomization but before dosing. (Cycle 1, 3)
Health Care Utilization	X	Health Care Utilization will be collected at each visit
Clinical Drug Supplies		
IRT Drug Vial Assignment	X	Within 24 hours prior to dosing
Administer Study Treatment	X	First dose to be administered within 3 days following randomization. See Section 4.3 .

Table 5.1-3: On-Study Assessments - Part 2 (CA209511)		

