4.3.2 Safety

Overall safety and tolerability will be measured by the incidence of adverse events, serious adverse events, AEs leading to discontinuation, deaths, specific laboratory abnormalities (worst grade) and changes from baseline in each treatment group. Toxicities will be graded using the National Cancer Institute (NCI) Common Terminology Criteria for Adverse Events (CTCAE) version 4.0. See details in the Core Safety SAP¹.

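### A first drug-related Grade 3-5 AE between day 31 after the last combination dose and the planned Part 2 start counts in the primary endpoint only if a Part 2 dose follows, and SAP 7.6.1 has no 100-day comparison to check this

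*Protocol*

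**What the plan says.** Protocol 8.3.1 and SAP 4.1 define the primary endpoint in the same way. A treated subject is a case if at least one drug-related AE of Grade 3 or higher occurred "with onset on or after the first dose of study treatment and within 30 days of the last dose of study treatment". The last dose means the last dose of any study treatment, so a Part 2 dose moves the end of the window.

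On the interval between the two parts, Protocol 4.5 says: "The first flat dose 480 mg nivolumab in Part 2 will be administered 6 weeks after the last combination dose in Part 1". Protocol 3.1.2 has the flat dose "beginning 6 weeks after the last combination dose, until progression or unacceptable toxicity", and Protocol 4.3.2 gives the same six weeks.

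Protocol 4.4.4 links some events to stopping: "Grade 3 drug-related uveitis, pneumonitis, bronchospasm, diarrhea, colitis, neurologic toxicity, hypersensitivity reaction, or infusion reaction of any duration requires discontinuation". It also exempts others: "Grade 3 drug-related laboratory abnormalities do not require treatment discontinuation except" for listed cases, and a Grade 3 endocrinopathy controlled by hormone replacement generally need not stop treatment.

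SAP 6.1.2 allows an on-treatment window of either 30 or 100 days, depending on the analysis. SAP 7.6.1 specifies one two-sided CMH test with IVRS strata and an adjusted difference, both on the 30-day endpoint. SAP 7.6.6 limits the by-period summaries to the 30-day window. General safety reporting is deferred: "See details in the Core Safety SAP" (SAP 4.3.2).

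**The concern.** The Part 1 to Part 2 transition is the only scheduled dosing interval longer than the 30-day window. Part 1 doses are 21 days apart and Part 2 doses 28, so the window bridges those intervals but not one of 42 days.

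Two subjects can have the same first event on the same day after the last combination dose and be classified differently because of what was done afterwards. Grade 3 colitis in the gap requires discontinuation and so goes uncounted. A controlled Grade 3 endocrinopathy in the gap can be followed by Part 2 and be counted. An unrelated reason can also prevent the later dose, such as progression on the first scan: "FIRST tumor assessment should be performed at 12 weeks" after randomization (Protocol Table 5.1-2), which lands inside the gap.

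This is the only endpoint that is formally tested (SAP 7.1). The supplied text gives no stratified comparison that would show whether the conclusion holds when these events are counted regardless of later dosing, and no count of how many there are.

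**Working it through.** **Dates.** Take the first dose as day 0 and assume on-schedule dosing.
- Cycle 4: 3 × 21 = day 63.
- 30-day window closes if no later dose is given: 63 + 30 = day 93.
- Cycle 5: 63 + 42 = day 105.
- Week-12 scan: 12 × 7 = day 84 from randomization (first dose within 3 days of it), between days 63 and 105.
- Span at issue: 42 − 30 = 12 days, that is, days 31 to 42 after the last combination dose. An onset on day 42 itself counts if the Part 2 dose is given that day. The span is longer if Part 2 is delayed.

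**Classification by day after the last combination dose** (Part 2, if given, on day 42)

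| Onset | Primary, no Part 2 dose | Primary, Part 2 dose given | Part 1 summary | Part 2 summary | 100-day window |
|---|---|---|---|---|---|
| 30 | counted | counted | in | out | counted |
| 31 | not counted | counted | out | out | counted |
| 41 | not counted | counted | out | out | counted |
| 42 | not counted | counted | out | in, if dosed | counted |

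The Part 1 summary closes at day 30 (SAP 6.1.2.1) and the Part 2 summary opens at the first Part 2 dose (SAP 6.1.2.2). An event between them appears in neither, even when it counts in the primary endpoint.

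**The plan's power.** Protocol 8.1 states 80% for 170 per arm, 40% vs 55%, two-sided 0.05. The normal approximation gives 79.4% with pooled variance and 80.0% unpooled, so the figure reproduces. Full enumeration of two Binomial(170) arms with the pooled z test (unstratified, standing in for CMH) gives 78.7%, the reference used below.

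**Illustration of size.** The documents give no frequency of events in the gap, so all of the following is assumed: constant hazard; true rates of 40% (A) and 55% (B) reached by day T; four on-schedule doses for everyone; and a share f of gap events with no later dose for any reason.

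Subjects lost per arm = 170 × f × (S^(93/T) − S^(105/T)), with S = 0.60 in A and 0.45 in B.
- T = 105: A 0.6361 − 0.6000 = 0.0361; B 0.4930 − 0.4500 = 0.0430.
- T = 365: A 0.8780 − 0.8633 = 0.0146; B 0.8159 − 0.7948 = 0.0211 (differences taken before rounding).

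| T (days) | f | Lost, A | Lost, B | Power |
|---|---|---|---|---|
| none lost | – | 0 | 0 | 78.7% |
| 105 | 1 | 6.1 | 7.3 | 76.8% |
| 105 | 0.5 | 3.1 | 3.7 | 77.7% |
| 105 | 0.25 | 1.5 | 1.8 | 78.2% |
| 365 | 1 | 2.5 | 3.6 | 75.9% |
| 365 | 0.5 | 1.2 | 1.8 | 77.3% |
| 365 | 0.25 | 0.6 | 0.9 | 78.0% |

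These are not upper bounds. With T = 105 and f = 1, and everyone's last combination dose at Cycle 1, the same formula over days 30 to 42 gives 8.3 (A) and 11.8 (B), because more subjects are still event-free.

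**Direction.** It is open. Freely chosen losses, in percentage points A/B, of 2/2 give 79.6%, 2/1 give 84.3% and 1/2 give 73.6%.

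**Follow-up for a 100-day window.** The trigger is: "The analysis of the primary endpoint will occur when all subjects who are still on-treatment have had at least 2 post-baseline tumor assessments" (Protocol 8.3.1). Two scans means week 12 + 8 = week 20, or day 140. At that point a last dose at Cycle 4 has 140 − 63 = 77 days of follow-up, and one at Cycle 5 has 140 − 105 = 35. At about 6 months (day 183, Protocol 3.1.3) these are 120 and 78. Visit X2 falls at 30 + 84 = day 114 after the last dose, or 100 to 128 with both ±7-day windows (Protocol Table 5.1-4). If the discontinuation date is day 42, X1 moves to that date and X2 to 42 + 84 = day 126.

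**The case against.** The strongest reply is that nothing here is an error. The 30-day window is explicit, identical in both documents, and matched to follow-up visit X1 at 30 days. That stands: a reader might infer a contradiction, and there is none.

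A second reply is that the Core Safety SAP may already tabulate drug-related AEs by grade and arm at 100 days. SAP 7.6.6 restricts only its additional by-period summaries to 30 days, which suggests that the main ones may not be so limited. That also stands, so the documents do not support saying that the trial has no 100-day safety analysis. What the supplied text lacks is a 100-day version of the stratified comparison in SAP 7.6.1 and a split by later dosing.

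Third, the numbers are small. For f of 0.25 to 0.5 the loss is 0.6 to 3.7 subjects per arm, and f = 1 is unrealistic because Protocol 4.4.4 exempts many qualifying events from stopping. A reader might infer from the unequal-loss cases that the test is biased or underpowered. Those losses were chosen freely and have no basis in the documents, so neither inference is supported.

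Fourth, Protocol 5.3 places Cycle 5 at Week 18, which might suggest a much longer gap. That parenthetical, in a laboratory schedule, stands alone against the six-week interval in Protocol 3.1.2, 4.3.2 and 4.5. The Week 16 in the footnote to Protocol Table 5.5.1-1 fits that interval, since day 105 is 15 elapsed weeks and so opens Week 16. Week 18 needs reconciling but does not support a larger estimate.

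Finally, a 100-day window also runs from the last dose, so it settles days 31 to 42 without removing the wider dependence on treatment duration.

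**Conclusion.** The mechanism holds by date arithmetic alone: for a first qualifying event in the gap, inclusion in the only tested endpoint depends on a dosing decision made after the event, sometimes because of it. Probably few subjects are affected. Neither the size nor the direction of any effect can be computed from the documents, and no power shortfall or bias is shown. The illustrated range of 0.6 to 6.1 subjects in Arm A and 0.9 to 7.3 in Arm B, with power of 75.9% to 78.2% against 78.7%, rests on the constant hazard, the on-schedule dosing and the chosen f and T. This is a worthwhile, cheap improvement: the check should be prespecified, because added after unblinding it would be post hoc.

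**What to change.** Keep the 30-day primary definition and its alpha. Before unblinding, add to SAP 7.6.1:
- A supportive analysis without alpha allocation that counts onset from first dose to 100 days after the last dose, with the same two-sided CMH test (IVRS strata) and adjusted difference with 95% CI, reported beside the 30-day result.
- By arm, the number of subjects whose first qualifying event began more than 30 days after the most recent dose, split by whether a later dose was given.
- By arm, the number of subjects off treatment whose 100-day follow-up is incomplete at the primary cut. Repeat the analysis once subjects off treatment at that cut have completed visit X2. A fixed date 100 days after the cut could precede X2 and miss events not yet recorded.
- A statement of whether the Core Safety SAP already gives 100-day tables of drug-related Grade 3-5 AEs by arm.

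Separately, reconcile the Week 18 label for Cycle 5 in Protocol 5.3 with the interval in Protocol 4.5.

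The cost is one SAP paragraph, two small tables and one later data cut. No new data are needed, since serious and nonserious AEs are already collected to 100 days (Protocol 6.1.1 and 6.2.1). The downsides are slightly higher absolute rates, harder attribution of late events after subsequent therapy, and a window that is still anchored to the last dose.
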